3.3. Research Approach

3.3.a Research Design Overview. We will conduct a randomized controlled trial, where upon enrollment participants will be randomized to either the *Guerreiras* intervention or to a wait-list control condition, in which participants will also receive the *Guerreiras* intervention after a one-year waiting period. We chose a wait-list control to safeguard ethical treatment of participants by ensuring that a potentially impactful intervention will be available to all after a brief waiting period. Rolling enrollment of 400 participants will take place over one year, with the intervention initiating activities as participants are assigned to a *Guerreiras* group (8-10 participants); group assignment will occur as soon as sufficient participants are enrolled. *Guerreiras* includes five group sessions over the course of 6-8

weeks, led by two peer navigators (PNs). Following group sessions, PNs will provide six months of peer navigation to each participant to support HIV testing (clinic or HIVST), PrEP uptake and persistence, harm reduction and other behavioral prevention as indicated, or HIV care (if participant tests positive). Groups will reconvene for a reunion session 3 months into navigation services (see Intervention Design 3.4). Follow-up data collection for the main

Figure 2: Study Design

trial phase will be conducted every three months, with comprehensive interviewer-administered surveys conducted at enrollment (baseline), 6 months (interim survey), and 12 months (endline), with brief monitoring surveys at the 3-month visits (e.g. 3- and 9-months) to assess prevention uptake (HIV testing, PrEP use, etc; see Figure 2, Study Design). This results in four post-enrollment follow-up visits per participant to document regular prevention uptake and two visits to document changes in stigma measures during the main trial phase. Qualitative interviews will be conducted with 18 participants at two timepoints (36 interviews total) to provide context to our exploration of intersectional stigma and gender affirmation, including how intersectional stigma impacts engagement with *Guerreiras* and HIV prevention uptake, how gender affirming programming impacts intersectional stigma, and insight into psychosocial mechanisms of change over time.

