3.5.a. Eligibility: Participants must be 18 years or older; assigned ‘male’ at birth but currently identify as female, transgender, transsexual, or *travesti* (a common term for trans women in Brazil); not be known to be HIV positive; be a resident of the São Paulo area; and consent for study procedures, including review of clinical records. In Brazil, language that trans women use to describe themselves includes cultural terms such as ‘*transsexuais*’, ‘*mulher trans*’, and ‘*travesti*’ among others. No restrictions will be placed on the degree to which the participant has transitioned legally or physically. Participants may be PrEP-naïve or have initiated PrEP; being on PrEP is not an exclusion criterion. While we do not anticipate encountering many trans women already taking PrEP, preliminary data indicate that a large proportion of trans women who initiate PrEP will struggle with persistence and require renewed engagement¹⁹. Based on current data, we expect a maximum of 5% to have initiated PrEP prior to enrollment. We will not require HIV testing to enter the study; any participant who enrolls and either discovers she is positive or seroconverts will remain enrolled with navigation focused on HIV treatment. Recruitment staff will use a brief screening tool to establish eligibility prior to enrollment.

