3.7 Measures

Primary Exposure: Randomization arm – intervention or wait-list control – will be considered the primary predictor variable for all primary analyses and recorded on study enrollment forms. Because the degree of engagement with the intervention will vary by individual, we will also capture intervention dose on study monitoring forms as a secondary exposure measure for additional (per protocol) analyses.

Primary Outcomes: (Evaluation: Aims 1 & 2): HIV testing uptake will be defined as any clinical evidence or report of HIV testing in each interval. This includes multiple data sources: documented HIV testing at a study clinic, report of having attended a non-study clinic for HIV testing, or evidence of HIVST kit receipt with self-report of HIVST use and/or documented HIVST use by the PN during a group or individual navigation session. The primary PrEP use outcome measure is PrEP *persistence*, which is the PrEP measure utilized for sample size calculations. We will document *PrEP initiation*, defined as a participant filling their first PrEP prescription, through PrEP dispensing information in the national SICLOM database. However, because initiation does not imply continued use, we will focus analyses of PrEP use on *PrEP persistence* – or documented use at every interval, defined as sufficient pill dispensation for complete 3-month coverage with no more than 10 days uncovered in the period. Secondary outcomes, including PrEP *adherence* and uptake of other prevention services (harm reduction, STI care) are listed in Table 3, below.

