Mediators: Intersectional Stigma: We will include a comprehensive suite of stigma measures that will be examined together in mediation and moderation analyses (see Analysis section 3.8). To explore the concept of intersectional stigma, we will analyze potential interactions between the stigma domains. This reflects the concept of intersectionality as more than an additive process of multiple stigmatized identities, but where experiences of multiple types of stigma create a confluence of interlocking systems of oppression that act synergistically as barriers to prevention and cannot be meaningfully interpreted independently. We will include quantitative measures of internalized, anticipated, and enacted stigma in the following domains: gender-related stigma, race-related stigma, stigma related to sex work and substance use, HIV and PrEP stigma. Stigma resilience is operationalized as coping self-efficacy and healthcare empowerment in the context of anticipated

and enacted stigma. Comprehensive surveys will be conducted at enrollment, interim, and endline at 6-month intervals; we do not expect changes in stigma every 3 months (interval for outcomes monitoring).

Covariates: We will measure demographic and other individual, social, and structural barriers or facilitators to care to assess potential covariates and confounders in analyses.

Table 3: Primary and Secondary Measures

Domain	Instrument/measure	Data source	Frequency of data collection/extraction
PRIMARY EXPOSURE			
Intervention	Randomization arm	Enrollment/study records	Continuous during enrollment
PRIMARY OUTCOMES			
HIV testing	Binary: Tested (HIVST or at a clinic) in past 3-months	Clinical data extraction; study records (HIVST); self-report (testing)	Extracted bi-annually, Continuous, Monitoring visits (3-monthly)
PrEP initiation	Binary: Initiation of PrEP in past 3-months*	National data (SICLOM)	Extract quarterly
PrEP persistence	Binary: PrEP dispensed with 80 or more days covered in 3-months per dispensation records*	National data (SICLOM)	Extract quarterly
SECONDARY OUTCOMES			
Prevention and service uptake	Uptake of harm reduction services	Self-report	Monitoring visits (3-monthly)
	STI referrals and treatment	Clinical data extraction; Self-report	Extracted bi-annually, Monitoring visits (3-monthly)
	Condom use (consistent use with regular and occasional partners and clients)	Clinical data extraction; Self-report	Extracted bi-annually, Monitoring visits (3-monthly)

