PrEP adherence	Drug levels	Dried blood spots	Monitoring visits (3-monthly)
SECONDARY EXPOSURE			
Intervention dose	Engagement with intervention (group sessions & navigation)	Study monitoring forms	Continuous
COVARIATES/MEDIATORS			
Demographics	Age, gender identity, SES, race, housing stability, mobility, employment, sex work	Self-report - Surveys	Comprehensive visits (6-monthly)
Intersectional stigma	Internalized, anticipated, and enacted stigma related to: Identity-based stigma: gender ⁹² , race ⁹³ Social position-based stigma: sex work ⁹⁴ , substance use Stigma-related barriers: HIV stigma ⁹⁵ , PrEP stigma ⁹⁶	Self-report - Surveys	Comprehensive visits (6-monthly)
	Stigma resilience: Coping self-efficacy ⁹⁷⁻⁹⁹ Healthcare empowerment ¹⁰⁰	Self-report - Surveys	Comprehensive visits (6-monthly)
Gender affirmation	Need for and experiences of gender affirmation ¹² Transgender group identity ⁹²	Self-report - Surveys	Comprehensive visits (6-monthly)
Social, structural barriers to / facilitators of prevention	Depression ¹⁰¹⁻¹⁰³ , substance use ¹⁰⁴ , social support ^{105,106} , social cohesion ^{107,108} , relationship violence ¹⁰⁹ , trauma ¹¹⁰ , access to clinical care and services received, food insecurity ^{111,112} .	Self-report - Surveys	Comprehensive visits (6-monthly)

*calculated among those with indications for PrEP use.

3.8 Data Analysis Plan and Statistical Procedures:

Preliminary analyses, missing data. Frequency tables for all variables and measures of central tendency and variability for continuous variables (e.g., stigma scores) will characterize the sample and will be stratified by randomization arm to check for imbalances. If arms differ significantly at baseline on one or more covariates, we will use causal modeling methods (e.g., propensity scores, targeted maximum likelihood estimation) to obtain the desired marginal effect estimates under the counterfactual assumption of balanced arms¹¹³⁻¹¹⁷. We will address incomplete data with multiple imputation (MI)¹¹⁸; MI makes the relatively mild assumption that incomplete data arise from a conditionally missing-at-random (MAR) mechanism¹¹⁹. Auxiliary variables will be included to help meet the MAR assumption^{120,121} and sensitivity analyses will be conducted with weighted MI¹²² to assess the robustness of the MAR assumption¹²³. SAS¹²⁴ and *Mplus*¹²⁵ will be used for analyses.

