Primary analyses for Aims 1 and 2. We expect HIV prevention outcomes to improve in the intervention arm relative to the control arm during the main trial phase. We hypothesize that, following the intervention, odds of HIV testing will be higher for intervention participants relative to control participants (Aim 1, Hypothesis 1). We also hypothesize that, following the intervention, the odds of PrEP initiation and persistence will be higher for the intervention group than for the control group (Aim 2, Hypothesis 2). Our primary interest is to estimate the marginal or population-average effects of intervention participation on these primary outcomes rather than the effect for a hypothetical average subject¹²⁶. Moreover, within-subject outcome correlations are considered nuisance parameters rather than quantities of interest to be modeled explicitly. Accordingly, generalized estimating equations (GEE) will be used for the primary analyses to test Hypotheses 1 and 2 using time-averaged comparisons of post-baseline (follow-up) measurements of intervention group with control group in the main trial phase. Alpha (α) will be set at .05 for these two planned comparisons. The alternating logistic

regression (ALR) approach implemented in SAS PROC GENMOD will be used to address the 3-level clustering of observations within participants and participants assigned to *Guerreiras* group leaders. This analysis will follow an intent-to-treat (ITT) approach by including all randomized participants. Further detail on the analytic model and secondary analyses, including secondary outcomes, intervention persistence, and intervention replicability, are included in Form E, Statistical Design and Power.

Primary Analyses for Aim 3. GEE will be used to test Aim 3 hypotheses that, following the intervention, relative to the control arm, intervention arm participants will have: 1) higher mean levels of resilience to anticipated stigma, 2) higher mean levels of resilience to enacted stigma, and 3) lower mean levels of internalized stigma. Analyses will follow the same ITT modeling approach as described above for Aims 1 and 2, except that a normal distribution and identity link will be employed to analyze continuous, normally-distributed stigma scores. These hypotheses will be tested via planned time-averaged comparisons of post-baseline measurements of the two arms in the main trial phase. These comparisons will be tested at $\alpha=.05$ per comparison.

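### PrEP initiation can occur only once but is scored afresh each quarter in a time-averaged GEE, so the planned odds ratio is for a first fill in an average quarter, not for initiating PrEP

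*Combined protocol and SAP*

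**What the plan says.** Section 3.7 gives initiation as "defined as a participant filling their first PrEP prescription", taken from the national dispensing database (SICLOM). Table 3 lists it under primary outcomes and scores it as "Binary: Initiation of PrEP in past 3-months", extracted quarterly. The table's footnote says that initiation and persistence are "calculated among those with indications for PrEP use".

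Section 3.8 states Hypothesis 2 as "the odds of PrEP initiation and persistence will be higher for the intervention group than for the control group". The method is GEE, fitted by alternating logistic regression (ALR), using "time-averaged comparisons of post-baseline (follow-up) measurements of intervention group with control group in the main trial phase". On the analysis set: "This analysis will follow an intent-to-treat (ITT) approach by including all randomized participants". Section 3.3.a fixes the number of repeats: "This results in four post-enrollment follow-up visits per participant to document regular prevention uptake".

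Section 3.5.a admits women already using PrEP and adds "we expect a maximum of 5% to have initiated PrEP prior to enrollment".

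Two further statements bear on the weight of the point. Section 3.7 names persistence as the primary measure of PrEP use and the basis of the sample size. Section 3.8 leaves further model detail to Form E, which is not among the documents.

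**The concern.** A first fill can happen once. A woman who starts in the first quarter scores 1, 0, 0, 0 and in her last three quarters is indistinguishable from a woman who never starts. The available text has no rule that takes her out of later quarters, no ever-initiated-by-month-12 variable, and no time-to-event model. A woman who initiated before enrolment can never score 1. The footnote on indications solves neither problem, because having an indication is not the same as never having started.

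Hypothesis 2 is worded as the odds of initiating PrEP, and section 3.8 says that the primary interest is in estimating population-average effects. If the stated rule is followed, the reported odds ratio answers a different question from the one a reader will take it to answer. The gap widens as uptake rises, so it is largest if many women start PrEP.

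**Working it through.** **The plan's own figures.** 400 × 0.75 = 300 analysed, or 150 per arm, as stated. The 8-point detectable difference in section 3.8 (control proportion 0.05) is for persistent PrEP use. No rate or detectable effect is given for initiation, so there is no initiation figure to reproduce.

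**Inputs.** Four post-baseline quarters (section 3.3.a); at most one positive quarter per woman (definition in section 3.7); up to 5% prior initiators (section 3.5.a). The 12-month initiation rates below are assumptions. The first pair borrows the 5% and the 8-point difference that the plan states for PrEP use.

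**Formulas.** Let C be the proportion of an arm with a first fill by month 12. With a fixed denominator, complete follow-up and one arm effect across quarters, the four quarterly proportions sum to C, so their average is C/4 and cannot exceed 25%. With odds(p) = p/(1 − p):

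- ever-initiated OR = odds(C_int) / odds(C_ctl)
- time-averaged OR = odds(C_int/4) / odds(C_ctl/4)
- discrete-time hazard OR (starters leave the risk set, constant hazard) = odds(h_int) / odds(h_ctl), with h = 1 − (1 − C)^(1/4)

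**Example, 20% v 40%.** Ever-initiated: (0.40/0.60)/(0.20/0.80) = 2.67. Time-averaged: (0.10/0.90)/(0.05/0.95) = 2.11. Hazard: h = 0.054 and 0.120, giving 2.37.

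| Assumed 12-month initiation, control v intervention | Risk ratio | Ever-initiated OR | Time-averaged OR | Hazard OR |
|---|---|---|---|---|
| 5% v 13% | 2.6 | 2.84 | 2.65 | 2.75 |
| 10% v 20% | 2.0 | 2.25 | 2.05 | 2.15 |
| 20% v 40% | 2.0 | 2.67 | 2.11 | 2.37 |
| 30% v 60% | 2.0 | 3.50 | 2.18 | 2.76 |

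The time-averaged OR lies close to the 12-month risk ratio. It is below the ever-initiated OR by 7% in the first row (1 − 2.65/2.84) and by 38% in the last (1 − 2.18/3.50).

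**Prior initiators.** With 5% structural zeros in each arm at 20% v 40%, the quarterly proportions become 0.95 × 0.05 = 0.0475 and 0.95 × 0.10 = 0.095. The OR is (0.095/0.905)/(0.0475/0.9525) = 2.10 rather than 2.11, so this part is numerically small.

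**Simulation check.** Logistic GEE with independence working correlation and robust standard errors, 150 per arm, 300 replicates per setting, no navigator clustering. Median GEE v ever-initiated OR: 2.62 v 2.81 (5% v 13%), 2.10 v 2.66 (20% v 40%), 2.20 v 3.52 (30% v 60%). Power was 0.647 v 0.650 in the first setting and 0.947 for both in the second. Type I error at 20% in both arms was 0.047 for both analyses. Moving starts earlier or later had no systematic effect on the GEE odds ratio.

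**The planned association model.** ALR describes within-person dependence by the pairwise odds ratio P11 × P00 / (P10 × P01). For a once-only event no two quarters can both be 1, so P11 = 0, the odds ratio is 0 and its log has no finite value. This does not arise for HIV testing or persistence, which can recur.

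**The case against.** The strongest reply is that the plan itself gives initiation a lesser place. Section 3.7 makes persistence the primary PrEP measure, says that analyses of PrEP use will focus on it, and sizes the trial on it. Section 3.8 sets alpha for two planned comparisons, which fits HIV testing plus one PrEP comparison. Persistence can properly be scored every quarter. This stands, and it limits the weight of the point. It does not remove it: initiation is still listed as primary in Table 3 and named in Aim 2 and in Hypothesis 2.

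Second, Form E may define the risk set or exclude prior users. That is possible, so the absence of a rule can be claimed only for the available text. Table 3 would still need to agree with whatever Form E says.

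Third, the quarterly odds ratio is a coherent quantity, and a hazard-type odds ratio would also differ from the 12-month one (2.37 v 2.67 at 20% v 40%). That is fair. The trouble is the mismatch with a hypothesis worded as the odds of initiating PrEP, not that only one odds ratio is legitimate.

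Fourth, the larger gaps rest on uptake rates that the documents do not give. At 5% v 13%, the pair nearest to a documented figure, the gap is small. This also stands.

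Fifth, the limit of C/4 needs a fixed denominator. The footnote does not say whether indication is set at baseline or reassessed each quarter. If it is reassessed, the arithmetic is approximate.

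**Conclusion.** The mismatch is in the text: a once-only definition, quarterly scoring, and a model that averages over all follow-up visits. Followed as written, it yields the odds ratio of a first fill in an average quarter, and it gives ALR a within-person association parameter that has no finite value for this outcome. The understatement relative to the ever-initiated odds ratio runs from slight (2.65 v 2.84) to large (2.18 v 3.50) over the assumed rates. It rests on a fixed denominator, complete follow-up and a common arm effect.

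A reader might infer that the test of Hypothesis 2 is invalid, that the trial loses power, or that its main PrEP result is compromised. The documents do not support this. In the simulations type I error and power were almost unchanged, and the lead PrEP measure and the power statement concern persistence. A reader might also take the fall in the risk difference to a quarter (20 points to 5 at 20% v 40%) as a reported error, but section 3.8 plans odds for this hypothesis, not a risk difference. What needs correcting is the effect estimate for a listed primary outcome. It should be settled before analysis.

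**What to change.** In Table 3 and section 3.8, score initiation once per woman: first SICLOM PrEP dispensing between randomisation and month 12, among women with no SICLOM PrEP dispensing before randomisation and with a PrEP indication fixed at baseline. Analyse it with a logit link, allowing for clustering by peer-navigator pair.

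An alternative is a discrete-time hazard model in which a woman leaves the risk set after her first fill. It should be reported as a hazard-type odds ratio, because its estimand differs from the 12-month odds ratio. Choose one and say which. Keep the repeated quarterly GEE/ALR for HIV testing and persistence, and bring Form E into line.

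The cost is a few lines of wording. Section 3.6.b already extracts dispensing dates from SICLOM, so no new data collection is needed; the extract must also cover the time before randomisation, and the baseline rule for indication must be written down. One minor loss is that prior users (up to 5%) leave the initiation analysis, though they remain in the persistence analysis.

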We will also explore whether stigma measures at interim (six-months) surveys mediate the relationship between intervention assignment and subsequent outcomes as well as whether combinations of stigmas measures at baseline and six-months act synergistically (interact) and moderate the exposure-outcome associations in order to assess intersectional stigma. We will also assess whether measures of gender affirmation and transgender group identity increase over the course of the intervention and mediate the relationship between intervention arm and subsequent outcomes. Further detail on Aim 3 secondary analyses, including mediation and moderation, are in Form E, Statistical Design and Power.

Statistical power. We computed minimum detectable effect sizes for primary outcomes using the two-group repeated proportions module in NCSS PASS 16¹²⁷. The study will begin with 400 participants equally allocated to two study groups. Assuming 25% attrition, data from 300 participants will be available for analysis at all time points. We further lowered the effective sample size (ESS) to account for correlations between participants receiving the intervention from the same *Guerreiras* PN pairs, using a range of plausible intraclass correlations (ICC)s within PN pairs. Assuming $\alpha=.05$ and $\text{power}=.80$, with four post-baseline measurements and assuming control group proportions $P_0=.50$ for HIV testing and $P_0=.05$ for PrEP use, we will have sufficient power to detect small to medium effects. This includes effects as low as 13% and 8% difference in proportion in HIV testing and persistent PrEP use, respectively, in the intervention arm compared to control. Effect size estimates for primary analyses (all Aims 1, 2, and 3) fall between cutoffs of .20 and .50 for small and medium standardized effect sizes¹²⁸. Statistical power is fully elaborated in Form E, Statistical Design and Power.

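### Table 3 limits the PrEP primary outcomes to participants with PrEP indications, section 3.8 analyses everyone randomized, and the supplied text does not say that indication is fixed before randomization

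*Combined protocol and SAP*

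**What the plan says.** Section 3.7 makes persistence the main PrEP outcome, "which is the PrEP measure utilized for sample size calculations". Table 3 scores it as "PrEP dispensed with 80 or more days covered in 3-months per dispensation records", taken from the national dispensing database (SICLOM). An asterisk on both the initiation and the persistence rows leads to the footnote "calculated among those with indications for PrEP use".

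Section 3.8, on the primary GEE analyses for Aims 1 and 2, states: "This analysis will follow an intent-to-treat (ITT) approach by including all randomized participants". It makes no exception for PrEP.

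The power paragraph of section 3.8 covers both primary outcomes: "Assuming 25% attrition, data from 300 participants will be available for analysis at all time points". It then lowers the effective sample size for clustering within peer-navigator pairs and for nothing else. It reports a detectable difference of 8 points in persistent PrEP use over a control proportion of 5%. It also says: "Statistical power is fully elaborated in Form E, Statistical Design and Power".

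Three other sections bear on who counts as indicated:
- Section 3.4.d expects about 5-10% not to be indicated, through contraindications and/or low risk.
- Section 3.4.c calls a participant's own wish for PrEP the leading indication.
- Section 3.5.b ties eligibility exams to interest in PrEP.

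None of these is a dated rule for an analysis denominator.

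**The concern.** A participant without an indication is outside the denominator under Table 3 and inside the analysis under section 3.8. Two analysts working from the supplied text could report different primary PrEP results, and a reader cannot tell which population the 5% and the 8 points describe.

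Timing matters more than size. The all-randomized set is fixed at randomization. The indicated set is fixed only if indication comes from information recorded by then. The intervention provides PrEP education, teaches participants to assess their own risk and supplies HIV self-tests (sections 3.4.b to 3.4.d). HIV testing is not required at entry, and participants found positive stay enrolled (section 3.5.a). If desire for PrEP, perceived risk or HIV status learned during follow-up decided who is indicated, membership of the denominator could differ between arms and the comparison would no longer be fully randomized.

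**Working it through.** **Inputs from the documents.** 400 randomized 1:1; 25% attrition; alpha .05; power .80; four post-baseline measurements; 5% control proportion and an 8-point difference (section 3.8); 5-10% not indicated (section 3.4.d); 16 navigators working in pairs, so 8 pairs (section 3.4.e).

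**Assumptions.** Two-sided test. The within-person correlation ρ and the intraclass correlation (ICC) are not in the supplied text, so I took ICC = 0, .01, .02 and .05 and solved ρ to match the stated power. Clustering is applied to the intervention arm only.

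**Formulas**, with n per arm:
- Repeated-measures factor V = (1 + 3ρ)/4
- Design effect D = 1 + (n/8 − 1) × ICC
- SE = √{V [p0(1 − p0) + D p1(1 − p1)]/n}
- Power = Φ[(p1 − p0)/SE − 1.96]

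**Step 1: the plan's own figures.** 400 × 0.75 = 300, so n = 150. Power of 80% for 5% v 13% needs SE = 0.08/(1.96 + 0.842) = 0.02855. With ICC 0, V = 0.02855² × 150/(0.0475 + 0.1131) = 0.76, so ρ = 0.68. ICC .01, .02 and .05 give ρ = .57, .48 and .29. The stated 8 points is therefore attainable, and nothing here shows an error in it.

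**Step 2: footnote set, with 5% v 13% among the indicated.** Example with ICC 0 and n = 135: SE = √(0.7616 × 0.1606/135) = 0.0301; 0.08/0.0301 − 1.96 = 0.70; power 75.7%. Ranges below run over the four ICC values.

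| Outcomes from | Indicated | N analysed | Power | Detectable difference (points) |
|---|---|---|---|---|
| 300 | 95% | 285 | 78.0-78.8% | 8.16-8.26 |
| 300 | 90% | 270 | 75.7-77.4% | 8.33-8.54 |
| 400 | 95% | 380 | 85.0-88.4% | 6.93-7.35 |
| 400 | 90% | 360 | 83.9-86.6% | 7.16-7.49 |

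The rows from 400 apply if SICLOM supplies outcomes for participants who miss visits.

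**Step 3: all-randomized set, same effect among the indicated.** If those not indicated never have PrEP dispensed, the contrast becomes 0.95 × 8 = 7.6 or 0.90 × 8 = 7.2 points.

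| Outcomes from | Indicated | Difference (points) | Power |
|---|---|---|---|
| 300 | 95% | 7.6 | 77.7% |
| 300 | 90% | 7.2 | 75.2% |
| 400 | 95% | 7.6 | 83.9-88.2% |
| 400 | 90% | 7.2 | 81.6-86.2% |

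Against Step 2 at N=300, the loss runs from under half a point of power to about 2 points.

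**Step 4: the other reading.** If 5% v 13% describes all randomized participants, the same data give 8/0.95 = 8.4 or 8/0.90 = 8.9 points among the indicated. Power for the restricted analysis from 300 is then 80-82%, so nothing is lost. Which reading applies is what the text leaves open.

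**Step 5: dependence on arm.** The documents give one overall share not indicated and none by arm, so no size can be put on this bias.

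**The case against.** The strongest reply is that the passages can be read together. The intent-to-treat sentence covers both aims and may mean only that participants are analysed as assigned, with each outcome scored as Table 3 defines it; the 300 may be a general planning figure. That reading is possible, but the sentence goes further and includes everyone randomized, without a PrEP exception, so the footnote still has to be reconciled with it.

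Form E is a fair point too. Section 3.8 sends further model detail and the full power account there, so the rule may exist. This limits the point to the supplied text.

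A reader might infer that the missing 5-10% deduction leaves the trial underpowered for PrEP. The documents do not support that: outcomes come from a national dispensing database, so a missed visit need not lose them, multiple imputation is planned, and the footnote set drawn from 400 exceeds 80% power. A reader might also take the 67% behavioral eligibility in section 3.1 as the indicated share; it comes from a Rio de Janeiro study, and this trial's own expectation is in section 3.4.d. Nor does anything supplied say that indication will be judged after randomization.

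Finally, the all-randomized analysis has slightly less power if the effect is confined to the indicated, and it answers a somewhat different question. Both are true. The reason to prefer it is that its denominator cannot depend on arm.

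**Conclusion.** The mismatch stands and concerns a primary outcome: the supplied text supports two denominators for PrEP persistence, and neither ties indication to baseline nor links the 8 points to one of them. Confidence is high on the wording conflict, and lower on whether a rule is missing altogether, because Form E was not available.

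At the protocol's own 5-10%, the numerical effect is modest: 76-79% power from 300 participants or 84-88% from 400, against the stated 80%. These figures rest on assumed ICC values, on ρ calibrated to the stated power, and on 5% v 13% holding among the indicated. No failure of the stated power is shown. Bias from a denominator set after randomization is a possibility that the plan should close off, not something demonstrated. This should be fixed because it is cheap and protects the randomized comparison.

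**What to change.** Make all randomized participants, the set section 3.8 already names, the primary denominator for PrEP persistence. Take the outcome from SICLOM, count participants without PrEP dispensing as not persistent, and state this as the chosen estimand. Keep the indicated analysis as secondary, defined by the same rule in both arms from information recorded at or before randomization.

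If the sponsor prefers the indicated set as primary, fix indication from pre-randomization data and restate the N and the detectable difference for that set.

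Either way, align the Table 3 footnote with the analysis and power paragraphs of section 3.8, say which set the 8 points describes, and carry over any rule already in Form E.

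The cost is mainly wording, since SICLOM data are already to be extracted quarterly (section 3.6.b). The downside is the slight dilution shown in Step 3. The baseline definition of indication will also be imperfect: HIV testing is not required at entry and eligibility exams depend on interest in PrEP, so some contraindications and undiagnosed infections will be missed. No new baseline tests are proposed.
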